7.1.2. Arm B: Relapsed/refractory DLBCL

The following assumptions will underlie the two-stage design for Arm B: At the end of induction response rate will be 50% with this combination, against a null hypothesis of 20%. With this 2-stage design, 9 patients will be enrolled in the first stage. If 2 or fewer respond among these 9 patients, accrual to this study arm will be stopped. Otherwise, 8 additional patients will be accrued in the second stage for a total of 17. The null hypothesis will be rejected if 7 or more responses are observed in 17 patients. This design yields a type I error rate of .05 and a power of .8 when the true response is 50%.

7.1.3 Arm C: Relapsed FL, Obinutuzumab +_Pembrolizumab

Arm C includes patients exposed to prior alkylating agent (including bendamustine) and rituximab therapy. The following assumptions will underlie the two-stage design for this arm: At the end of induction response rate will be 70% with this combination (similar to that observed with obinutuzumab and chemotherapy³¹, against a null hypothesis of 45% (as observed with single-agent obinutuzumab³⁵. With this 2-stage design, 12 patients will be enrolled in the first stage. If 5 or fewer respond among these 12 patients, enrollment to this study arm will be stopped. Otherwise, 13 additional patients will be accrued in the second stage for a total of 25. The null hypothesis will be rejected if 16 or more responses are observed in 25 patients. This design yields a type I error rate of .04 and a power of 0.80 when the true response is 70%. Patients with stable disease and clinical benefit, as determined by the treating investigator, or response qualifying as PR or CR, will be permitted to proceed to the extended dosing phase in Arm C.

7.2. Study Stopping Rules

7.2.1. Arms A and B

We plan to enroll a total of up to 37 patients on Arms A and B of this study. The study will be suspended and referred to the institutional Data Safety Monitoring Committee (DSMC) for consideration of results and appropriate modification or termination of the study if there is sufficient evidence that the probability of death (due to any cause other than disease progression) exceeds 10%, or if more than 50% of patients experience a serious adverse event (SAE).

This will be deemed to occur if the lower level of a one-sided 80% confidence interval for death proportion exceeds 10% or SAE proportion exceeds 50% at any time. Operationally, the study will be suspended in the following circumstances:

• If 2 out of the first 8 or fewer patients, 4 out of the first 16 or fewer, 5 out of the first 24 or fewer, 6 out of the first 32 or fewer, or 7 out of the 37 or fewer patients experience death for any reason other than disease progression, or

• If 6 out of the first 8 or fewer, 11 out of the first 16 or fewer, 16 out of the first 24 or fewer, 20 out of the first 32 or fewer, or 23 out of the 37 or fewer patients experience serious adverse events.

In summary, the following will lead to suspension of accrual:

• Non-disease-progression death rate > 10% (2/8, 4/16, 5/24, 6/32, 7/37).

• SAE occurring in >50% of patients (6/8, 11/16, 16/24, 20/32, 23/37)

If the true probability of death due to causes other than the underlying disease is 5%, then the probability of suspending the trial due to excess death after 16, 24, and 32 patients is approximately 0.01, < 0.01, < 0.01, respectively. If the true probability of death is 25%, the probability of suspension due to excess death is approximately 0.73, 0.84, and 0.90, respectively.

If the true probability of grades III-IV AE is 30%, the probability of suspending the trial due to excess AEs after 16, 24, and 32 patients is approximately 0.01, 0.01, and <0.01, respectively. If the true probability of AE is 70%, the probability of suspension due to excess AE is approximately 0.73, 0.82, and 0.91, respectively. (Probabilities of suspension estimated from 5,000 simulations).

Accrual after suspension may continue after DSMC review, and if the DSMC permits a protocol revision to allow further accrual that may permit the study to address its objectives while maintaining a favorable safety profile.

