6.4	Reporting of Pregnancy and Lactation to Merck	46
Ducto col v/ 0 1	atad 21 July 2021	and 2 of (2

6.5	Reporting Requirements for Adverse Events/Adverse Reactions
6.6	Serious Adverse Events46
6.7	Reporting of Events of Clinical Interest (ECI)47
6.8	Evaluating Adverse Events
6.	8.1 Sponsor-Investigator Responsibility for Reporting Adverse Events
7.0	STATISTICAL ANALYSIS PLAN
8.0	LABELING, PACKAGING, STORAGE AND RETURN OF CLINICAL SUPPLIES
8.1	Investigational Product
8.2	Packaging and Labeling Information57
8.3	Clinical Supplies Disclosure
8.4	Storage and Handling Requirements
8.5	Returns and Reconciliation
9.0	Data and Safety monitoring plan58
10.0	RECORDS
11.0	REGULATORY RESPONSIBILITIES OF SPONSOR-INVESTIGATOR59
12.0	APPENDICES60
12.1	ECOG Performance Status60
12.2	Common Terminology Criteria for Adverse Events V4.0 (CTCAE)60

TRIAL SUMMARY

[figure not shown]
Abbreviated Title	Pembrolizumab and CD20-Directed Therapy in relapsed/refractory FL and DBLCL	
Trial Phase	II	
Clinical Indication	FL and DLBCL who have relapsed or refractory follicular or diffuse large B cell lymphoma	
Trial Type	Nonrandomized, three-arm prospective clinical trial	
Type of control	N/a	
Route of administration	IV	
Trial Blinding	N/a	
Treatment Groups	A) Relapsed/refractory FL (pembrolizumab and rituximab), B) Relapsed/refractory DLBCL ineligible or declining autologous stem cell transplant (pembrolizumab and rituximab),	
	C) Relapsed/refractory FL (pembrolizumab and obinutuzumab)	
Number of trial subjects	Total 62 A) up to 20 patients, B) up to 17 patients, C) up to 25 patients	
Estimated enrollment period	24 months	
Estimated duration of trial	48 months	
Duration of Participation	48 months	
Estimated average length of treatment per patient	16 months	

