7.0 STATISTICAL ANALYSIS PLAN

This study administers therapy to two groups of patients, relapsed/refractory FL and relapsed/refractory DLBCL.

Subjects who fail to complete study therapy or withdraw consent before the first response assessment for reasons other than disease progression, death, SAE, or drug-related adverse events will be replaced, to allow response assessment in accordance with study stopping rules. The first group (Arm A) includes patients with relapsed or refractory follicular lymphoma, and will include at least 9 patients with rituximab-refractory disease.

The second group (Arm B) consists of patients with relapsed/refractory diffuse large B-cell lymphoma ineligible for, or failing to respond to or progressing, after autologous stem cell transplantation.

These groups will employ independent rules, using Simon's two-stage design, and accrual will be suspended for review if futility thresholds are met. Two-stage designs which limit the maximum sample size will be considered. Once enrollment is suspended, the nature of events to leading to stopping will be assessed by the Principal Investigator and reported to institutional regulatory authorities, in accordance with the institutional Data Safety Monitoring Plan. The institutional Data Safety Monitoring Committee will determine whether any further accrual may proceed. Statistical analysis will entail descriptive statistics. Categorical variables will be summarized by number and percentage, and continuous variables will be summarized by min/median/max/mean/sd, respectively. Overall response rate, and response quality, will be evaluated according to CT criteria and PET/CT in relevant patients, as per the 2014 Lugano criteria.²⁸ PFS/OS distribution will be estimated and Kaplan-Meier curves will be presented. Log-rank testing and Cox proportional hazard regression models might be applied to evaluate the association between survival endpoints and prognostic factors. To compare continuous variable in the correlative studies, student's t-test and regression analysis might be applied if deemed appropriate.

Subjects who fail to complete study therapy before the first response assessment for reasons other than disease progression, death, SAE, or drug-related adverse events will be replaced, to allow response assessment in accordance with study stopping rules.

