7.2.2 Arm C

We plan to accrue at most 25 patients to Arm C, testing the combination of obinutuzumab and pembrolizumab. As with arms A and B, accrual to this arm will be suspended and referred to the institutional Data Safety Monitoring Committee (DSMC) for consideration of results and appropriate modification or termination of the study if there is sufficient evidence that the probability of death (due to any cause other than disease progression) exceeds 10%, or if more than 50% of patients experience a serious adverse event (SAE).

For Arm C the following will lead to suspension of accrual:

- Non-disease-progression death rate > 10% (2/8, 3/15, 4/23).
 - i. If the true probability is 5%, the probability of suspension is approximately 3.9% (probabilities estimated from 5,000 simulations).
 - ii. If the true probability is 35%, the probability of suspension is approximately 91.7% (probabilities estimated from 5,000 simulations).
- SAE occurring in > 50% of patients (3/3, 4/5, 5/6, 6/8, 7/10, 8/12, 9/13, 10/15, 11/17, 12/19, 13/21, 14/22, 15/24)

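### The death and SAE suspension rules pool Arms A and B, so toxicity confined to the DLBCL arm is diluted: at the plan's own excessive rates the pooled rule suspends about half the time (deaths) or one time in five (SAEs)

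*Combined protocol and SAP*

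**What the plan says.** The trial summary gives the arm sizes as "A) up to 20 patients, B) up to 17 patients, C) up to 25 patients". Section 7.2.1 treats the first two as one safety population: "We plan to enroll a total of up to 37 patients on Arms A and B of this study". The study is suspended and referred to the DSMC when the "lower level of a one-sided 80% confidence interval for death proportion exceeds 10% or SAE proportion exceeds 50% at any time". This is turned into counts on the combined sequence of patients: 2/8, 4/16, 5/24, 6/32 and 7/37 for deaths not due to progression, and 6/8, 11/16, 16/24, 20/32 and 23/37 for SAEs. Each count applies to that number of patients or fewer.

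The operating characteristics are given for a single common rate. At the high end for deaths: "If the true probability of death is 25%, the probability of suspension due to excess death is approximately 0.73, 0.84, and 0.90, respectively", after 16, 24 and 32 patients. For adverse events at 70% the figures are 0.73, 0.82 and 0.91. The acceptable rates used are 5% (deaths) and 30% (adverse events).

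Arm C is handled separately in section 7.2.2, which opens its own list with "For Arm C the following will lead to suspension of accrual". No section gives a safety count for Arm B alone.

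**The concern.** A rule on a combined count responds to the average of the two arms. If non-progression deaths or SAEs are excessive in Arm B and acceptable in Arm A, Arm A patients enlarge the denominator and hold the count below its limit. The published suspension probabilities do not describe that case, because they hold only if both arms share one rate. A DSMC relying on them would expect about a 0.9 chance of a trigger at the excessive rate, when the chance for a problem in one arm could be far lower. At stake is whether up to 17 DLBCL patients could be enrolled at a toxicity rate the plan regards as too high without the numerical rule prompting a DSMC review.

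**Working it through.** **Inputs.** From the trial summary and section 7.2.1: 20 patients in Arm A, 17 in Arm B, the pooled counts above, the excessive rates (25% deaths, 70% SAEs) and the acceptable rates (5%, 30%). Assumptions not given in the documents: Arm A sits at the acceptable rates, and patients arrive in random order. The plan words its adverse-event operating characteristics in terms of grade III–IV AEs; they are read here as applying to the SAE rule.

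**Method.** Exact recursion. After *i* patients let *b* be the number from Arm B and *k* the number with an event. The next patient comes from Arm B with probability (17 − b)/(37 − i) and has an event with that arm's rate. The trial suspends as soon as *k* reaches the limit for the next listed look. Checking after every patient gives the same result as checking at the listed looks.

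**Step 1: reproduce the plan's figures (equal rates).**

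| Rate in both arms | After 16 | After 24 | After 32 | Stated |
|---|---|---|---|---|
| Deaths 25% | 0.730 | 0.835 | 0.902 | 0.73, 0.84, 0.90 |
| SAEs 70% | 0.729 | 0.817 | 0.909 | 0.73, 0.82, 0.91 |

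The method matches. At 5% deaths in both arms, however, the cumulative probability is 0.06, where the plan states about 0.01 or less. The stated values fit single-look tails (0.007, 0.006, 0.005). That is a separate matter, but it explains the 0.06 baseline used below.

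**Step 2: what the pooled rule sees when the rates differ.**

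- Deaths: (20 × 0.05 + 17 × 0.25)/37 = 5.25/37 = 14.2%.
- SAEs: (20 × 0.30 + 17 × 0.70)/37 = 17.9/37 = 48.4%, below the 50% limit.

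As an illustration, SAEs in 16 of 17 Arm B patients and 6 of 20 Arm A patients give 22/37, one short of the final limit. Spread evenly over accrual, they cross no earlier limit either.

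**Step 3: suspension probability by 37 patients.**

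| Scenario | Deaths | SAEs |
|---|---|---|
| Pooled rule, B excessive, A acceptable, random order | 0.49 | 0.19 |
| Same, all of Arm A first | 0.31 | 0.06 |
| Same, all of Arm B first | 0.75 | 0.73 |
| Same, Arm A stops for futility at 7 | 0.65 | 0.43 |
| Same, Arm B stops for futility at 9 | 0.29 | 0.08 |
| Random order, Arm A lower (0% deaths; 20% SAEs) | 0.33 | 0.08 |
| Random order, Arm A higher (10% deaths; 50% SAEs) | 0.64 | 0.59 |

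**Step 4: like-for-like comparator.** Apply the plan's one-sided 80% lower limit (Clopper-Pearson) to Arm B alone. Lower limits are 10.4% for 2/8 deaths, 13.8% for 4/17 (9.2% for 3/17), 53.8% for 6/8 SAEs and 51.5% for 11/17 (45.7% for 10/17). The Arm B limits are therefore 2/8 and 4/17 for deaths, and 6/8 and 11/17 for SAEs.

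| Arm B alone, 17 patients | Suspends |
|---|---|
| Deaths 25% | 0.76 |
| Deaths 5% | 0.06 |
| SAEs 70% | 0.81 |
| SAEs 30% | 0.013 |

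Pooling thus lowers detection from 0.76 to 0.49 for deaths and from 0.81 to 0.19 for SAEs.

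**The case against.** Grouping safety by regimen is defensible. Arms A and B receive the same drugs on the same schedule (section 4.2, Table 2), while Arm C uses a combination that section 3.1.5 says had not been studied before. Nor does pooling contradict section 7.0: the sentence "These groups will employ independent rules, using Simon's two-stage design" concerns the futility design, not safety. Both points stand. They explain the choice but do not supply operating characteristics for unequal rates.

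A reader might infer from the poor prognosis described in sections 3.1 and 3.1.2 that Arm B should be expected to have more toxicity. The documents do not support that. Those passages describe lymphoma outcome, the death rule excludes progression, and section 6.6 excludes progression events from SAE reporting. Unequal rates are a possibility the rule should handle, not a prediction.

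A reader might also set 0.49 and 0.19 against the stated 0.90 and 0.91. That exaggerates the loss, because the stated figures are for 32 patients all at the excessive rate. For deaths, about a third of that gap (0.90 − 0.76 = 0.14 of 0.41) comes from Arm B having only 17 patients.

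The two rules also act together. If deaths and SAEs are both excessive in Arm B, at least one triggers with probability about 0.59 if they are treated as independent, or about 0.55 if deaths also count as SAEs.

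Finally, the investigator's ongoing review, the at least annual committee and IRB review (section 9.0) and early termination for a safety hazard (section 4.6) remain. They carry no arm-specific threshold, but an unsafe arm would not go unreviewed.

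**Conclusion.** The concern holds as one of dilution. At the plan's excessive rates in Arm B and acceptable rates in Arm A, with random accrual order, the pooled rule suspends with probability about 0.49 (deaths) and 0.19 (SAEs), against 0.76 and 0.81 for the same criterion on Arm B alone.

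The stronger reading, that excess toxicity in Arm B would usually go undetected, holds for SAEs at 30%/70% but not for deaths, where the result is close to a coin flip. At 15% deaths in Arm B the pooled rule suspends in only 0.23, but an Arm B rule would reach only 0.41, so pooling is not the sole cause there.

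The size depends on Arm A's true rates and on accrual order, neither of which the documents give. Across the scenarios above the pooled figures run from 0.29 to 0.75 for deaths and from 0.06 to 0.73 for SAEs. That protection depends so much on which arm fills first is itself a weakness. The gap is in rule-triggered DSMC review, not in all safety oversight.

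**What to change.** Keep the pooled rule and add an arm-specific trigger, at least for Arm B, on the plan's stated one-sided 80% criterion: deaths in 2 of the first 8 or fewer, or 4 of 17 or fewer; SAEs in 6 of the first 8 or fewer, or 11 of 17 or fewer. The trigger suspends that arm and refers it to the DSMC. Section 7.2.1 should also report suspension probabilities for unequal arm rates.

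With the Arm B trigger added, under random order:

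| Rates (A / B) | Pooled rule only | Plus Arm B trigger |
|---|---|---|
| Deaths 5% / 25% | 0.49 | 0.78 |
| SAEs 30% / 70% | 0.19 | 0.82 |
| Deaths 5% / 5% | 0.06 | 0.10 |
| SAEs 30% / 30% | 0.01 | 0.02 |
| Deaths 10% / 10% | 0.25 | 0.34 |
| SAEs 50% / 50% | 0.25 | 0.35 |

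The change needs SAP wording and counting by arm, and no extra patients. The price is more reviews when toxicity is acceptable or at the limit. Because section 7.2.1 lets accrual resume after DSMC review, a false alarm need not end the arm.

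Triggers in both arms modelled on Arm C's list (deaths 2/8, 3/15, then 4/20 for A or 4/17 for B; SAEs 6/8, 10/15, then 12/19 for A or 11/17 for B) cost more. Any-suspension becomes 0.16 at 5% deaths in both arms, 0.04 at 30% SAEs, and 0.48 and 0.47 at the 10% and 50% limits. For toxicity confined to Arm B they reach about 0.83 on each rule, little better than the Arm B trigger alone, though they would also cover excess toxicity confined to Arm A.

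### Section 7.2.1: the Arms A and B suspension counts do not implement the stated one-sided 80% criterion; at the block ends, four of the ten are one event too high against it

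*Combined protocol and SAP*

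**What the plan says.** Section 7.2.1 sets the safety suspension rule for up to 37 patients in Arms A and B. The criterion is an interval limit: "This will be deemed to occur if the lower level of a one-sided 80% confidence interval for death proportion exceeds 10" per cent "or SAE proportion exceeds 50% at any time. Operationally, the study will be suspended in the following circumstances". Counts by block follow, for deaths not due to progression (for example "4 out of the first 16 or fewer, 5 out of the first 24 or fewer, 6 out of the first 32 or fewer") and for SAEs. They are repeated under "In summary, the following will lead to suspension of accrual" as "Non-disease-progression death rate > 10% (2/8, 4/16, 5/24, 6/32, 7/37" and "SAE occurring in >50% of patients (6/8, 11/16, 16/24, 20/32, 23/37". No interval method is named.

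The section also reports suspension probabilities from 5,000 simulations. For a 5% death rate, "the probability of suspending the trial due to excess death after 16, 24, and 32 patients is approximately 0.01, < 0.01, < 0.01, respectively". For a high rate, "If the true probability of death is 25%, the probability of suspension due to excess death is approximately 0.73, 0.84, and 0.90, respectively". For a 70% SAE rate it gives 0.73, 0.82 and 0.91.

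Section 7.2.2 applies the same 10% and 50% limits to Arm C with a finer set of counts (2/8, 3/15, 4/23 deaths; 3/3, 4/5 and so on to 15/24 SAEs) and names no interval.

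**The concern.** The counts are presented as the working form of the criterion, so they should be the smallest event numbers at which the 80% lower limit passes 10% or 50%. Several are larger than that. A criterion that applies at any time also cannot be carried by one count for a whole block of patients.

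Staff will follow the counts, which are given twice. Data that the same section treats as sufficient evidence could then fail to reach the Data Safety Monitoring Committee (DSMC), and two readers could classify the same data differently. Arm C, with the same limits, would be suspended on some data that leave Arms A and B open.

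**Working it through.** **Inputs.** All come from section 7.2.1: level 80% one-sided; limits 10% (deaths) and 50% (SAEs); the ten counts; block ends 8, 16, 24, 32, 37. The Arm C counts come from section 7.2.2.

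**Step 1: reproduce the plan's own figures.** I took the list as a sequential boundary (a count reached at or before its block end suspends) and computed cumulative suspension by exact binomial recursion. After 16, 24 and 32 patients:

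- 25% deaths: 0.730, 0.835, 0.902 (published 0.73, 0.84, 0.90)
- 70% SAEs: 0.729, 0.817, 0.909 (published 0.73, 0.82, 0.91)

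The high-rate figures therefore describe the list as printed.

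**Step 2: counts implied by the criterion.** The exact one-sided 80% lower limit for x events in n patients is the 0.20 quantile of Beta(x, n − x + 1). It exceeds p0 exactly when P(X ≥ x | n, p0) < 0.20. The limit columns show one event fewer than the list requires.

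| n | Deaths listed | Deaths implied | Limit one below list | SAEs listed | SAEs implied | Limit one below list |
|---|---|---|---|---|---|---|
| 8 | 2 | 2 | 1/8: 2.8% | 6 | 6 | 5/8: 41.6% |
| 16 | 4 | 4 | 3/16: 9.75% | 11 | 11 | 10/16: 48.8% |
| 24 | 5 | 5 | 4/24: 9.7% | 16 | 15 | 15/24: 51.8% |
| 32 | 6 | 6 | 5/32: 9.8% | 20 | 19 | 19/32: 50.4% |
| 37 | 7 | 6 | 6/37: 10.7% | 23 | 22 | 22/37: 51.2% |

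So 6/37 deaths and 15/24, 19/32 and 22/37 SAEs already meet the criterion (tail probabilities 0.160, 0.154, 0.189, 0.162), but the list asks for one more event.

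**Step 3: other interval methods at one-sided 80%.**

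- Wilson, Wald, Jeffreys, mid-p and Agresti-Coull all give 2, 3, 4, 5, 6 deaths and 6, 10, 15, 19, 22 SAEs, so 8 of the 10 listed counts are too high. A uniform-prior limit also puts 8 too high.
- Continuity-corrected Wald gives 3, 4, 5, 6, 7 deaths and 6, 11, 15, 19, 22 SAEs: three counts too high and one (2/8) too low.

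None of the eight methods reproduces the list. All eight give 15, 19 and 22 SAEs at 24, 32 and 37.

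**Step 4: between block ends.** I used exact limits from n = 3 and required at least 2 deaths, because 1/1 and 1/2 would otherwise qualify with limits of 20.0% and 10.6%. Pointwise, ignoring earlier triggers, the list needs one more death than the criterion at 26 of 35 sample sizes, and 1 to 5 more SAEs at 32 of 35. Two sequences that the list does not stop:

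- Deaths in patients 5, 11 and 15: at patient 15 the limit for 3/15 is 10.4%. The criterion and Arm C's 3/15 are met; the list needs 4.
- SAEs in patients 2, 3, 5, 7, 8, 9, 11 and 12: at patient 12 the limit for 8/12 is 50.3%. The criterion and Arm C's 8/12 are met; the list needs 11.

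**Step 5: Arm C.** For each of its 16 pairs, the listed n is the largest at which that count still passes the exact one-sided 80% limit (for example 4/23: 10.15%; 4/24: 9.7%).

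**Step 6: effect on suspension probability by 16, 24 and 32 patients** (criterion as in step 4).

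| True rate | List | Criterion |
|---|---|---|
| 25% deaths | 0.73, 0.84, 0.90 | 0.81, 0.90, 0.95 |
| 70% SAEs | 0.73, 0.82, 0.91 | 0.83, 0.93, 0.97 |
| 5% deaths | 0.059, 0.061, 0.062 | 0.072, 0.080, 0.084 |

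The published 5% death figures (0.01, <0.01, <0.01) match neither column. The first block alone gives P(at least 2 of 8) = 0.057. The published values resemble single-look tails: P(at least 4 of 16) = 0.007, 5 of 24 = 0.006, 6 of 32 = 0.005.

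**The case against.** The strongest reply is that the counts are deliberate and the sentence is wrong. The published high-rate probabilities match the counts, and all ten counts equal a Wilson, Jeffreys or Agresti-Coull limit at one-sided 90%, which is the lower end of a two-sided 80% interval. A slip over sidedness would explain the block-end differences. This is plausible, and it stands as a reason not to assume which side governs. It does not remove the contradiction. It also does not rescue the any-time wording: against Wilson 90% limits from n = 3 (at least 2 deaths), the list still needs one more death at 21 of 35 sizes and 1 to 4 more SAEs at 28 of 35.

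Second, no method is named, and four of ten is the exact-limit result. This is right in part. Continuity-corrected Wald removes the 7/37 mismatch, but it then requires 3/8 deaths where the list has 2/8. The three SAE mismatches hold under every 80% method tried.

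Third, the counts are clear to staff, each block-end gap is one event, and suspension means DSMC review, not termination. That limits the harm but does not make the rule consistent.

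Fourth, Arm C names no interval, so carrying the exact method over to Arms A and B is an inference. That is fair; the finding does not depend on it.

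**Conclusion.** The concern holds. The listed counts do not implement the criterion they are said to implement. With exact limits, 1 of 5 death counts and 3 of 5 SAE counts are one event too high at the block ends, and the discrepancy reaches 5 SAEs between them. At a 25% death rate or a 70% SAE rate, the list suspends by 16 to 32 patients with probability about 0.05 to 0.11 lower than the criterion would. The published 5% death figures are too low for the list as well: about 0.06 cumulative, against 0.01 or less.

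The criterion probabilities rest on exact limits, a start at n = 3 and a two-death minimum, none of which the plan states. All probabilities assume independent patients whose outcomes are known when counted. Section 6.2 collects events to 90 days after the last pembrolizumab dose, so no number of extra patients enrolled is claimed. Because this is the quantitative safety trigger for up to 37 patients, it must be corrected. The documents do not settle whether the sentence or the list is the error.

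**What to change.** Reconcile the sentence and the counts in section 7.2.1. State the interval method, the level and the first patient number at which the rule applies. Any one of these would do:

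- **(a) Keep the criterion and replace the counts.** With exact limits and at least 2 deaths: deaths 2/8, 3/15, 4/23, 5/31, 6/37; SAEs 3/3, 4/5, 5/6, 6/8, 7/10, 8/12, 9/13, 10/15, 11/17, 12/19, 13/21, 14/22, 15/24, 16/26, 17/28, 18/30, 19/32, 20/34, 21/35, 22/37.
- **(b) Keep the blocks and change four counts** to 6/37 deaths and 15/24, 19/32 and 22/37 SAEs (the last two death blocks then merge). Replace the any-time wording with a statement that the limit is evaluated at block ends and that reaching a count earlier suspends at once.
- **(c) Keep the counts** and correct both the 80% level and the any-time wording, with a reason for differing from Arm C.

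Under each option, keep the provision that a count reached before its block is full suspends. With the (b) death counts, dropping it would delay suspension in 82% (20% deaths) to 85% (25% deaths) of suspended trials, by about 3 patients in those delayed. Recompute the published probabilities in every case, including the 5% death figures.

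Cost, as probability of suspension by 37 patients:

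| True rate | List, also (c) | (a) | (b) |
|---|---|---|---|
| 5% deaths | 6.2% | 8.5% | 6.5% |
| 10% deaths | 25.4% | 35.5% | 28.5% |
| 25% deaths | 92.2% | 96.3% | 94.9% |
| 30% SAEs | 1.2% | 5.4% | 1.3% |
| 50% SAEs | 24.8% | 45.0% | 31.5% |
| 70% SAEs | 93.3% | 97.7% | 96.5% |

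Option (a) brings clearly more reviews when the true rate sits on the limit, and (b) fewer than (a). Option (c) changes no operating characteristic.

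### The stated probabilities of suspending for excess deaths do not follow from the listed rules: at a 5% death rate they are about 6% in Arms A/B (stated 0.01 or less) and 8.0% in Arm C (stated 3.9%)

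*Combined protocol and SAP*

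**What the plan says.** Section 7.2.1 pools Arms A and B (up to 37 patients). It suspends accrual when non-progression deaths reach 2 in the first 8 or fewer patients, 4 in 16, 5 in 24, 6 in 32 or 7 in 37. At a true death rate of 5% it gives the probability of "suspending the trial due to excess death after 16, 24, and 32 patients is approximately 0.01, < 0.01, < 0.01". At 25%, "the probability of suspension due to excess death is approximately 0.73, 0.84, and 0.90, respectively".

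For serious adverse events (SAEs) the limits are 6/8, 11/16, 16/24, 20/32 and 23/37. At a true rate of 30% the section gives the probability of "suspending the trial due to excess AEs after 16, 24, and 32 patients is approximately 0.01, 0.01, and <0.01"; at 70% it gives 0.73, 0.82 and 0.91. The 30% sentence opens "If the true probability of grades III-IV AE is 30"%, although the rule counts SAEs.

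Section 7.2.2 gives the Arm C death rule as "Non-disease-progression death rate > 10% (2/8, 3/15, 4/23"). Its operating characteristics are "If the true probability is 5%, the probability of suspension is approximately 3.9"% and "If the true probability is 35%, the probability of suspension is approximately 91.7"%. Both sections attribute their probabilities to 5,000 simulations.

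**The concern.** At a 5% death rate the chance of two or more deaths among eight patients is already near 6%. A rule that contains that look cannot have an overall suspension probability of 1% after 16 patients, nor of 3.9% in Arm C. A cumulative probability also cannot fall as patients are added, yet the 5% line for Arms A/B goes from 0.01 to below 0.01.

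These are the plan's only stated operating characteristics for its death rules. They tell the IRB and the Data Safety Monitoring Committee (DSMC) how often a regimen with an acceptable death rate would be halted for review, and how reliably a harmful one would be caught. If the Arm C figures belong to a different rule, it is also unclear which rule was intended.

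**Working it through.** **Inputs.** Boundaries and true rates are as printed in Sections 7.2.1 and 7.2.2. Suspension occurs when the count reaches r among the first n patients.

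**Method.** Exact binomial recursion. At each look, add the probability of first reaching the boundary there, drop those paths, and carry the rest forward. Checking after every patient gives the same totals, because a count of r reached before patient n is still at least r at n.

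**Step 1: reproduce the plan's correct figures (Arms A/B, after 16, 24, 32 patients).**

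| Line | Stated | Cumulative | Single-look tail |
|---|---|---|---|
| Death, 25% | 0.73, 0.84, 0.90 | 0.730, 0.835, 0.902 | 0.595, 0.753, 0.847 |
| SAE, 70% | 0.73, 0.82, 0.91 | 0.729, 0.817, 0.909 | 0.660, 0.725, 0.867 |

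Both lines reproduce as cumulative probabilities and not as single-look tails. That fixes the basis in use.

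**Step 2: Arms A/B deaths at 5%.**

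- Look at 8: P(X ≥ 2) = 1 − 0.95⁸ − 8(0.05)(0.95⁷) = 1 − 0.6634 − 0.2793 = 0.0572.
- Added at 16: P(0 in first 8)·P(≥4 in next 8) + P(1 in first 8)·P(≥3 in next 8) = 0.6634(0.00037) + 0.2793(0.00579) = 0.0019. Cumulative 0.0591.
- Added at 24: 0.0018, cumulative 0.0609. Added at 32: 0.0012, cumulative 0.0621. By 37: 0.0624.

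The stated 0.01, <0.01, <0.01 agree instead with the isolated tails P(X ≥ 4 of 16) = 0.0070, P(X ≥ 5 of 24) = 0.0060 and P(X ≥ 6 of 32) = 0.0046. Those leave out the look at 8 patients.

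**Step 3: Arm C deaths.**

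| True rate | After 8 | After 15 | After 23 | Stated |
|---|---|---|---|---|
| 5% | 0.0572 | 0.0721 | 0.0801 | 0.039 |
| 35% | 0.831 | 0.951 | 0.988 | 0.917 |

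At 5%, the amount added at 15 is 0.6634(0.00376) + 0.2793(0.04438) = 0.0149. At 35%, it is 0.0319(0.4677) + 0.1373(0.7662) = 0.1201.

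No subset of the three looks gives both stated figures (5% / 35%):

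- 2/8 only: 0.057 / 0.831
- 3/15 only: 0.036 / 0.938
- 4/23 only: 0.026 / 0.982
- 2/8 and 3/15: 0.072 / 0.951
- 2/8 and 4/23: 0.071 / 0.986
- 3/15 and 4/23: 0.046 / 0.985

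The listed rule reaches 3.9% only at a death rate near 3.5%, and 91.7% only near 26%.

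**Step 4: simulation error.** The standard error is √[p(1 − p)/5000]: 0.0033 at 0.059, 0.0038 at 0.080 and 0.0016 at 0.988. The stated values lie about 15, 11 and 45 standard errors away.

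**Step 5: SAE line at 30%.** The exact cumulative values are 0.0120, 0.0121 and 0.0121, so the third figure should read 0.01 and not <0.01. The standard error at 0.0121 is 0.0015, so a simulated value just below 0.01 would be about 1.4 standard errors low.

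**The case against.** The best defence for Arms A/B is that the section never calls its probabilities cumulative and that the 5% figures are right as single-look tails. That probably explains where they came from, but it does not rescue them. The 25% line beside them is cumulative, nothing tells the reader that the basis changes, and the look left out causes nearly all the false suspensions.

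For Arm C, the true rate may be the misprint and not the rule: Section 7.2.1 uses 25% as its high death rate, and at 25% the listed Arm C rule gives 90.1%, much nearer to 91.7%. The gap is still beyond simulation error and the 5% figure stays wrong, but the sponsor's check should cover the 35% as well as the rule.

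Section 7.2.1 also defines the trigger through an 80% lower confidence limit applied at any time. Taken literally with exact limits after every patient, that would suspend more often at 5% (about 15% by 37 patients), so it moves further from the stated 0.01. The 0.06 belongs to the operational list.

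Three limits on the point stand. The third SAE figure could be simulation noise if the sample sizes were simulated separately, which the plan does not say. The adverse-event wording has no numerical effect. The practical consequence is bounded: suspension depends on observed counts, and "Accrual after suspension may continue after DSMC review", although this requires the DSMC to permit a protocol revision, and termination is also open to it.

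**Conclusion.** The concern holds. On the listed boundaries, false suspension for death at a 5% rate is about 6% in Arms A/B (roughly 1 in 16, stated as 1 in 100 or fewer) and 8.0% in Arm C (1 in 12.5, stated as about 1 in 26). Detection in Arm C at 35% is 98.8%, better than the stated 91.7%. The absolute gaps are about 5, 4.1 and 7.1 percentage points.

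The calculation assumes independent patients with a common true rate, outcomes known at each look, and the operational lists as the rules in force. The 25% death line and the 70% SAE line are correct. The thresholds, efficacy tests and sample sizes are unaffected. Which rule, sample size or death rate produced the Arm C figures cannot be settled from the documents.

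**What to change.** - **Arms A/B:** restate the 5% death line as 0.06, 0.06, 0.06 after 16, 24 and 32 patients. Leave the 25% line as it is. Label all these probabilities as cumulative over the listed looks and, with that label, change the third SAE figure at 30% to 0.01.
- **Arm C:** confirm that 2/8, 3/15, 4/23 is the death rule in force and that 5% and 35% are the intended rates. If so, restate the figures as 8.0% and 98.8%. If not, print the intended rule or rates with figures computed from them.
- **Event wording:** the listed rule counts SAEs, so use that term in the Section 7.2.1 operating-characteristic sentences in place of the adverse-event wording, once the sponsor confirms that this is the event meant.

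The cost is a text correction plus one check by the sponsor for Arm C. The false-suspension rates will look less favourable than those now printed. The correction itself requires no change to any threshold.
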